Empiric therapy with intravenous cefotaxime (or equivalent) is to be started as soon as the cell counts are available and continued for 5 days; appropriate subjects can be treated with ofloxacin (or equivalent) for 8 days. Subjects eligible for empiric therapy include those with culture-positive neutrocytic ascites, culture-negative neutrocytic ascites, and monomicrobial non-neutrocytic bacterascites. Empiric therapy in subjects with culture-positive neutrocytic ascites is modified based on the culture and sensitivities. Subjects who develop a recurrence of SBP at any time after the resolution of the current episode of SBP are to have a repeat paracentesis and if the polymorphonuclear (PMN) cell counts are ≥ 250 cells/mm³ and/or clinical signs of SBP are present, the subject is to have empiric therapy, which is to be modified as needed when the culture and sensitivities are available. All episodes of SBP up to Study Day 91 are to be treated using this algorithm.

- Intravenous ceftriaxone (or other 3rd generation cephalosporin) for 7 days or norfloxacin twice daily for 7 days (or equivalent) is to be given to prevent bacterial infections in subjects who have gastrointestinal bleeding (variceal bleeding) between Study Day 1 and Study Day 91.
- Subjects who survived a prior episode of SBP prior to entering the VTL-308 study or the episode of SBP was treated while the subject was in the VTL-308 study will be started on long-term prophylaxis with daily norfloxacin (or trimethoprim-sulfamethoxazole or equivalent); if indicated, long-term antibiotic prophylaxis can be started at Randomization or following an episode of SBP that occurred between Study Day 1 to Study Day 91.
- Subjects with cirrhosis and ascites but no gastrointestinal bleeding are to be started on long-term prophylaxis with daily norfloxacin (or trimethoprim-sulfamethoxazole or equivalent) if the ascitic fluid protein is <1.5 g/dL and at least one of the following is present: serum creatinine ≥ 1.2 mg/dL, BUN ≥ 25 mg/dL, serum sodium ≤ 130 mEq/L, and Child-Pugh ≥ 9 points with bilirubin ≥ 3 mg/dL.

5.4.1.9 ***Standard of Care - Thrombocytopenia***

Subjects with a platelet count $<20,000/\text{mm}^3$ without any clinical manifestations of bleeding during study treatment (ELAD and Control) will receive platelet transfusions based on the judgment of the clinical team. If the platelet count is $<20,000/\text{mm}^3$ and there are clinical manifestations of only localized contained bleeding, the subjects (ELAD and Control) must receive platelet transfusions. Subjects with a platelet count of $<20,000/\text{mm}^3$ and generalized bleeding are to be promptly assessed and, if on ELAD, considered for treatment discontinuation.

5.4.1.10 ***Standard of Care – ICU Discharge***

Subjects may be admitted to the ICU (or SDU where hospital standards allow and VTL approves) before or during the VTL-308 study. Therefore, the subjects' status should be continuously reviewed to identify subjects who no longer require ICU care. It is recommended that subjects be discharged from the ICU when their physiologic status has stabilized or when their physiological status has deteriorated and further interventions are not warranted. It is recommended that subjects experiencing alcohol withdrawal receive ICU care until their detoxification stage has stabilized (i.e., absence of seizures and delirium requiring intense monitoring). In addition, the subject experiencing alcohol withdrawal should be hemodynamically stable prior to discharge (i.e., not requiring intense monitoring for vasopressor administration or mechanical respiratory support). Continuous and frequent follow-up with the subject is recommended on the SDU or medical/surgical unit post-ICU discharge. For discharge from the ICU, a general guideline is that the subject is no longer in need of vasopressors, mechanical ventilation, or continuous extracorporeal renal treatment.

5.4.1.11 ***Standard of Care – Hepatic Hydrothorax***

Hepatic hydrothorax is defined as a large pleural effusion (usually unilateral and right-sided) that occurs in a subject with cirrhosis and ascites. The protein concentration in the pleural fluid is usually higher than in the ascitic fluid due to differences in the hydrostatic forces in the abdomen versus the chest. First-line therapy of hepatic hydrothorax consists of dietary sodium restriction and diuretics while TIPS is considered to be second-line treatment when it becomes refractory. Chest tube insertion is contraindicated in a subject with hepatic hydrothorax.

5.4.2 **Pre-Treatment**

Assessments will be carried out for both ELAD and Control subjects. For ELAD subjects, these assessments will be conducted in accord with [Section 5.4.2.1.1](#) to determine eligibility for extracorporeal safety. For Control subjects, these assessments will be conducted as part of Study Day 2 evaluations in accord with [Section 5.4.2.2.1](#).

5.4.2.1 ***Pre-ELAD Treatment***

Prior to initiation of the extracorporeal treatment, ELAD subjects will be evaluated in accord with [Section 5.4.2.1.1](#).

5.4.2.1.1 ***Pre-ELAD Safety Assessments***

Either the principal investigator or sub-investigator trained on the study must have evaluated the safety eligibility results and be immediately available when ELAD treatment begins in order to assess changes in the subject's condition since Randomization. This is especially important when evaluating changes during the 24 hours preceding initiation of ELAD treatment in order to

determine whether the subject remains eligible for extracorporeal treatment. When the ELAD Specialist confirms that ELAD treatment can begin in 6 hours or less, certain key safety factors must be evaluated. The following procedures will be completed ([Table 3](#)), and assessed in accord with the pertinent Exclusion Criteria [2](#), [3](#), [4](#), [7](#), [9](#), [10](#), [15](#), and [16](#) relative to the safety evaluation time point:

- Platelet count
- International Normalization Ratio (INR)
- Serum creatinine
- Evidence of infection unresponsive to antibiotics
- Hemodynamic instability assessment (blood pressure and MAP)
- Bleeding status
- Status with respect to ventilation, intubation, or need for hemodialysis

In addition the following will be done:

- Vital signs (blood pressure, heart rate, respiration rate, and temperature)
- Blood samples will be obtained for culture (×2) (See [Section 5.6.1](#))
- Total bilirubin will be obtained and MELD scores will be calculated in accord with [Section 5.2.4](#)
- Partial thromboplastin time (PTT) will be re-evaluated to guide anti-coagulation protocols (See [Section 5.5.2.1](#))

The ELAD Specialist and the Investigator or designee, prior to the initiation of ELAD treatment, will review the safety eligibility criteria listed above to ensure that the criteria are met, and that it is safe to initiate treatment. In addition, the Investigator or designee must confirm that the subject remains eligible for extracorporeal treatment. If these criteria are not met, the Sponsor Representative must be notified and ELAD treatment may not be initiated. The Medical Monitor or the Chief Medical Officer must be contacted by the Investigator or designee prior to initiation of ELAD treatment. All such procedures and evaluations must be recorded in the appropriate section(s) of the eCRFs.

Every effort must be made to initiate ELAD treatment as soon as possible after confirmation of the safety procedures. However, if treatment is delayed for any reason such that the time from the conduct of safety procedures is greater than 6 hours, the subject must be reassessed prior to the initiation of ELAD treatment in accord with the procedures above. In that case, the latest data would be recorded on the eCRF.

If the subject is no longer considered eligible for ELAD treatment, the ELAD cartridges will either be destroyed according to the institution's practices, or may be returned to VTL or designee. The reason the subject was deemed a Pretreatment Failure will be noted on the appropriate eCRFs. Pretreatment failure in the ELAD group will result in exclusion from the mITT population.

5.4.2.2 ***Pre-Control Treatment***

Control subjects undergo the same evaluation as ELAD subjects in order to standardize data collection.

5.4.2.2.1 ***Pre-Control Safety Assessments***

Either the principal investigator or sub-investigator trained on the study must have evaluated the safety eligibility results and be available at the safety eligibility evaluation timepoint for Control subjects (End of Study Day 2) (± 6 hours) in order to assess changes in the subject's condition since Randomization. The following procedures will be completed ([Table 3](#)), and assessed in accord with the pertinent Exclusion Criteria [2](#), [3](#), [4](#), [7](#), [9](#), [10](#), [15](#), and [16](#) relative to the safety evaluation time point:

- Platelet count
- International Normalization Ratio (INR)
- Serum creatinine
- Evidence of infection unresponsive to antibiotics
- Hemodynamic instability assessment (blood pressure and MAP)
- Bleeding status
- Status with respect to ventilation, intubation, or need for hemodialysis

In addition the following will be done:

- Vital signs (blood pressure, heart rate, respiration rate, and temperature)
- Blood samples will be obtained for culture ($\times 2$) (See [Section 5.6.1](#))
- Total bilirubin will be obtained and MELD scores will be calculated in accord with [Section 5.2.4](#)

All such procedures and evaluations must be recorded in the appropriate section(s) of the eCRFs.

If the subject is no longer considered eligible, the reason the subject was deemed a Pretreatment Failure will be noted on the appropriate eCRFs. Pretreatment failure in the Control group will result in exclusion from the mITT population.

5.4.3 **Treatment Start**

5.4.3.1 ***ELAD Treatment Start***

Prior to ELAD treatment initiation, subjects will be given 100 mg hydrocortisone (or institutional equivalent) and 50 mg diphenhydramine (or institutional equivalent). The timing for premedication should be in accord with the institution's policy for premedication; if ELAD cartridges need to be replaced premedication does not need to be repeated. Anticoagulation therapy should be considered prior to initiation of ELAD treatment (See [Section 5.5.2.1](#)).

The clinical, laboratory, and hemodynamic assessments will be performed at specified intervals during the study treatment period for both the ELAD and Control groups. An overview of evaluations during study treatment is presented in [Table 2](#) for Control subjects and [Table 3](#) for ELAD subjects.

The Investigator or designee should assess the subject, per their Institutions SOC guidelines for placing a patient on an extracorporeal system, immediately prior to starting the ELAD System blood pump.

All ELAD System management and cartridge placement will be done by ELAD Specialists. Site staff will not be responsible for the management of the ELAD System.

As ELAD may provide some degree of liver function, the dosage of drugs known to be subject to liver metabolism should be carefully monitored by the Investigator or designee in accord with institutional standard of care.

5.4.3.1.1 Catheter Placement

Prior to initiation of ELAD treatment, a dedicated, dual-lumen, kink-resistant dialysis catheter must be placed by an experienced physician, preferably ultrasound-guided, into the right internal jugular vein (preferred site), left internal jugular, femoral, or subclavian veins. If available and accessible, the interventional radiology team should be involved in complicated cases. Catheters should be designed to deliver a minimum of 300 mL/min blood flow to the ELAD System. For insertion and care of the catheter, the Centers for Disease Control and Prevention (CDC) or the European CDC guidelines (or local equivalent) should be followed.

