7.2 POPULATIONS

7.2.1 Safety

This population is defined as all subjects who are randomized and begin treatment including standard of care; analyses of this population will be based on actual treatment received. This population will include all randomized subjects assigned to the group that most accurately reflects the actual treatment that they received.

As a practical matter this means that a subject deemed an “ELAD-treatment initiation failure” that received no ELAD treatment would be assigned to the Control group. A subject that was randomized to the Control group yet received ELAD treatment would be assigned to the ELAD group.

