- Presence of significant increase in RBCs in the urine not related to the subject's renal disease, Foley catheters, etc.
- Urine hemoglobin levels of 3+ or 4+, if not present at these levels at Baseline

Expected Adverse Reactions for ELAD Treatment

According to the literature and previous protocols using either artificial or bio-artificial liver support systems, AEs in the following five categories might be expected to be encountered during treatment.

General Risks of Fractionated Plasma Filtration

- Higher risk of bleeding due to anticoagulation and/or unfavorable effects on the coagulation system. Specifically, in liver failure subjects, where hemostasis is disturbed, the use of plasma filtration or dialysis can precipitate bleeding.
- Hypotension
- Acute transient complement activation, leukopenia, thrombocytopenia, eosinophilia
- Hemolysis due to mechanical destruction of RBCs during whole blood perfusion through the ultrafiltrate generator
- Clotting within the extracorporeal blood circuit and in the ultrafiltrate generator
- Hypersensitivity: for example, an acute reaction may be observed similar to that known as first use syndrome reaction observed in patients undergoing dialysis
- Loss of valuable substances, including proteins, hormones, nutrients, electrolytes due to either dilution or binding to components of the tubing set
- Temperature disorders (e.g. hypothermia) (Biggers 1977; Chiu 2006; VitaGen, CR-202 CSR, 2004).

General Risks Associated With Using Heparin-Based Anticoagulation

- Heparin-induced thrombocytopenia
- Bleeding due to heparin ([Hirsch 2001](#))

General Risks Associated With Using Central Venous Catheters

The general risks associated with central venous catheters may occur during insertion, while they are indwelling, and during extraction ([Kusminsky 2008](#)).

- Insertion complications (pneumothorax, malpositioning, vascular injuries, dysrhythmias, neurological complications, lymphatic complications, and guide wire loss)
- Indwelling complications (infection, thrombosis, occlusion, vascular erosion and perforation, as well as catheter fracture and embolization)
- Extraction complications (air embolism, catheter breakage or separation from hub, and catheter knotting)

General Risks Associated With Administration of Albumin

- Rash/allergic reactions
- Hypotensive episodes/shock
- Fever
- Risk of transfusion-associated infections

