8.2 EXTENT OF EXPOSURE

For subjects who receive ELAD treatment, the duration of ELAD treatment will be calculated based on the start date/time of ELAD treatment (defined as the time at which the ultrafiltrate pump is switched on for the first time) to the end date/time of ELAD treatment (defined as the time at which the Ultrafiltrate pump is switched off for the last time). A second analysis will exclude any off-time gaps >6 hours (e.g., for cartridge exchange). The duration of ELAD treatment will be summarized by descriptive statistics and by proportions of subjects receiving <72 hours, 72 to <96 hours, and ≥96 hours of treatment. The mean time from Randomization to ELAD treatment initiation will also be presented using descriptive statistics.

For subjects who receive SOC treatment, the treatment start date will be the same as the randomization date.

Additionally, the proportions of subjects who completed at least 72 hours and 120 hours on ELAD treatment will be presented, along with the reason for discontinuation of ELAD treatment.

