8.3 ADVERSE EVENTS

The number and percent of subjects with treatment-emergent adverse events (TEAEs), TEAEs leading to ELAD discontinuation, TEAEs leading to ELAD treatment interruptions, TEAEs classified by their highest relationship to study drug, and TEAEs classified by their maximum severity, will be summarized by treatment group and by MedDRA System Organ Class and Preferred Term. Individual listings of all TESAEs, all deaths, and all TEAEs leading to ELAD discontinuation/interruption will be prepared.

Treatment-emergent adverse events are defined as those AEs with an onset date/time on or after the randomization date/time. The rationale for this is that subjects in both treatment groups are receiving standard of care at the time of Randomization. In addition summary tables of TEAEs and TESAEs will be presented based on treatment and post-treatment study periods. The study periods used in analysis for ELAD-treated subjects will be defined as Pre-ELAD (Randomization date/time to ELAD start date/time), ELAD Treatment (ELAD start date/time to Study Day 7), D8-D14 (Study Day 8 to Study Day 14) and D15-D91 (Study Day 15 to Study Day 91); and for Control subjects, Rand-D2 (Randomization date/time to Study Day 2), D3-D7 (Study Day 3 to Study Day 7), D8-D14 (Study Day 8 to Study Day 14) and D15-D91 (Study Day 15 to Study Day 91). Additional summaries of TEAEs that started between Randomization and ELAD treatment start, and TEAEs/TESAEs that started after ELAD treatment start will be presented by MedDRA System Organ Class and Preferred Term for subjects in the ELAD treatment group. For comparison purposes within these summary tables, TEAEs that started between Randomization and Study Day 2, and TEAEs/TESAEs that started after Study Day 2 will be presented for subjects in the Control treatment group.

Treatment-emergent adverse events will be coded using Medical Dictionary for Regulatory Activities (MedDRA) (Version 18.1) and incidences will be compared between treatment groups using MedDRA Preferred Terms within System Organ Classes. Subjects will only be counted once within each level of summarization.

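### ELAD-catheter insertion harms that begin before the pump starts are tabulated as Pre-ELAD events, or as Control events if ELAD is never started

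*Protocol*

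**What the plan says.** **Catheter.** Protocol 5.4.3.1.1: "Prior to initiation of ELAD treatment, a dedicated, dual-lumen, kink-resistant dialysis catheter must be placed by an experienced physician". Protocol Appendix D, under its heading on expected adverse reactions for ELAD treatment, says that "AEs in the following five categories might be expected to be encountered during treatment". One of the five categories is central venous catheters, and its first entry is "Insertion complications (pneumothorax, malpositioning, vascular injuries, dysrhythmias, neurological complications, lymphatic complications, and guide wire loss".

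**Attribution.** Protocol section 9 asks sites to separate ELAD-catheter complications from those of other central lines. Sections 9.2 and 9.6 and Appendix D treat the procedure, alongside the cells and the device, as part of the product to which an event can be attributed.

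**Start of ELAD.** SAP 8.2 takes the start as "defined as the time at which the ultrafiltrate pump is switched on for the first time". SAP 3.3 and 7.1.4 use the same definition.

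**Periods.** SAP 8.3 gives ELAD-treated subjects "Pre-ELAD (Randomization date/time to ELAD start date/time), ELAD Treatment (ELAD start date/time to Study Day 7" and gives Control subjects "Rand-D2 (Randomization date/time to Study Day 2), D3-D7 (Study Day 3 to Study Day 7". Further tables show events before and after ELAD start, set beside a Study Day 2 split in Control. SAP 8.3 also says: "Treatment-emergent adverse events are defined as those AEs with an onset date/time on or after the randomization date/time".

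**Non-starters.** Protocol 7.2.1 says that a subject randomized to ELAD "that received no ELAD treatment would be assigned to the Control group". SAP 3.4 has the same rule, and SAP section 8 uses this population for safety analyses by default.

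**The concern.** The protocol regards catheter insertion as part of what an ELAD subject is exposed to. The SAP's exposure clock starts later, when the pump is switched on, and no rule carries insertion events forward. The tables meant to isolate harm after ELAD starts can therefore omit a harm that the protocol requires only ELAD subjects to risk. Entry criteria allow platelet counts down to 40,000/mm³ and INR up to 2.5 (protocol 4.4), so bleeding at insertion is a realistic possibility.

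An excess of such events in the Pre-ELAD table could be taken for a chance imbalance before treatment. For a subject who is catheterized and then not started, the as-treated rule goes further: a harm of the ELAD procedure is counted against Control. Safety is part of the primary objective of this open-label pivotal trial, so the exposure tables should match the protocol's own description of the product.

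**Working it through.** The point turns on definitions. The plan states no figure to reproduce, so the check is to put the time points in order and see where each onset lands. The order is randomization, catheter placement (before initiation, protocol 5.4.3.1.1), then first pump-on (ELAD start, SAP 8.2).

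| Recorded onset | Where SAP 8.3 puts it | Set beside |
|---|---|---|
| After insertion, before pump-on, time recorded | Pre-ELAD | Control, randomization to Day 2 |
| Day of pump-on, time missing | ELAD Treatment, because SAP 8.1 imputes the ELAD start time | Control, Days 3 to 7 |
| After pump-on (for example a later catheter-site infection) | ELAD Treatment or a later period | Control, Days 3 to 7 or later |
| Any, in a catheterized subject never started | Control column (SAP 3.4) | Not applicable |

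The first two rows show an inconsistency: the same event falls in different periods according to whether its clock time was written down.

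**What still captures a starter's event.** Treatment-emergent events count from randomization, so the overall and highest-relationship tables in SAP 8.3 include it. The bleeding tables (SAP 8.3.1.3) and the serious-infection tables (SAP 8.3.1.1.2) use a first window from randomization to Day 7 that is not cut at pump-on. The bleeding terms in SAP Appendix D include catheter-site haematoma and haemorrhage. No special-interest term list in the SAP includes pneumothorax or a dysrhythmia, so for those only the overall and relatedness tables and the serious-event listing remain.

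**Can a non-starter already have the catheter?** The safety check is triggered when treatment can begin within 6 hours and is repeated if the start slips beyond 6 hours (protocol 5.4.2.1.1). A further assessment comes immediately before the blood pump starts (5.4.3.1). Nothing says whether the catheter goes in before or after these checks. Protocol 7.1 does expect some subjects randomized to ELAD not to be treated.

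**Illustrative size.** None of these inputs is in the documents; all are assumptions: insertion-complication risk 3% to 10%; ELAD subjects never started 10% to 20%; half of those already catheterized. Every complication is taken to have a timed onset before pump-on, with one event per subject.

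- Starters, 75 treated: 75 × 0.03 = 2.25 to 75 × 0.10 = 7.5 events in Pre-ELAD.
- Catheterized non-starters, 75 randomized: 75 × 0.10 × 0.5 = 3.75 to 75 × 0.20 × 0.5 = 7.5 subjects. These are people, not harms.
- Events moved to Control: 3.75 × 0.03 = 0.11 to 7.5 × 0.10 = 0.75.

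The figure 75 cannot be both the number treated and the number randomized. If 75 are randomized, 60 to 67.5 start, giving 60 × 0.03 = 1.8 to 67.5 × 0.10 = 6.75 events among starters. If 75 are treated, 75/0.90 = 83.3 to 75/0.80 = 93.75 are randomized. Then 8.3 to 18.75 do not start, 4.2 to 9.4 of them are catheterized, and 0.13 to 0.94 events move to Control. The conclusion is the same either way.

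**The case against.** The strongest reply is that these are supplementary tables. The SAP counts the events as treatment-emergent, attributes them to a component of the product, and shows bleeding, the most obvious worry, in a window not cut at pump-on. The Pre-ELAD table is laid out by Preferred Term, and a term such as catheter-site haemorrhage points to its own source. Serious events are listed individually, and every randomized subject has a narrative (SAP section 9), including non-starters. Platelets and INR are rechecked before start. All of this stands, and it limits the consequence.

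The reply also defends the boundary. Pump-on is objective and used consistently. Control is cut at Day 2 because that approximates when ELAD starts (SAP section 8). Moving only the ELAD boundary back to catheter placement or premedication would lengthen the ELAD window relative to Control's. Premedication timing also follows each institution's policy (protocol 5.4.3.1). This stands too, and is a good reason not to move the boundary.

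It does not answer the point itself. No rule brings timed procedure events into the exposure period. For non-starters, the overall and special-interest tables use the same Safety population, so they repeat the assignment to Control.

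**Conclusion.** The point holds, within limits. ELAD-catheter or procedure events with a recorded onset between insertion and pump-on are tabulated as Pre-ELAD. In a catheterized non-starter, if there are any, they count as Control events in the Safety population. The effect is confined to the period-split and before/after-start tables and to that assignment. The efficacy analysis of the ITT population is untouched.

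A reader might infer that insertion harms drop out of safety reporting, or that all of them land in the wrong period. The documents do not support either: starters' events stay in the overall and relatedness tables, delayed events fall after pump-on, and same-day events without a time are imputed to ELAD start. A reader might also infer that ELAD's safety profile is materially flattered. The direction is right, but the size is not established. The assumed inputs give about 2 to 8 starters' events and fewer than one event moved to Control, and the second figure also needs the catheter to precede a failed check. This is a modest correction, worth making because it is cheap and specific.

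**What to change.** 1. Keep first pump-on as the period boundary in SAP 8.2 and 8.3. Add to SAP 8.3 that adverse events the investigator attributes to the ELAD catheter or the ELAD procedure, with onset after catheter placement, are counted in the ELAD Treatment period and in the tables of events after ELAD start, even when onset precedes pump-on.
2. In the adverse-event tables, show subjects catheterized for ELAD but never started in a separate column for ELAD procedure only, not in Control.

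The cost is SAP wording and one small extra column. The first change uses attribution the protocol already asks sites to record. It needs no insertion clock time, since an event caused by the ELAD catheter must follow its placement; that helps because the documents do not show that an insertion time is captured. The second needs only the fact of placement, which should be available from the procedures recorded from randomization (protocol 8.3.3). The main drawback is that the exception relies on investigators' attribution in an open-label trial, so a footnote should give the number of events it moves.
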